9.3.2. Serious Adverse Event

An SAE is any untoward medical occurrence that at any dose:

- Results in **death** – includes all deaths, even those that appear to be completely unrelated to study drug (eg, a car accident in which a patient is a passenger).
- Is **life-threatening** – in the view of the investigator, the patient is at immediate risk of death at the time of the event. This does not include an AE that had it occurred in a more severe form, might have caused death.
- Requires in-patient **hospitalization** or **prolongation of existing hospitalization**. In-patient hospitalization is defined as admission to a hospital or an emergency room for longer than 24 hours. Prolongation of existing hospitalization is defined as a hospital stay that is longer than was originally anticipated for the event, or is prolonged due to the development of a new AE as determined by the investigator or treating physician.
- Results in persistent or significant **disability/incapacity** (substantial disruption of one's ability to conduct normal life functions).
- Is a **congenital anomaly/birth defect**
- Is an **important medical event** - Important medical events may not be immediately life-threatening or result in death or hospitalization, but may jeopardize the patient or may require intervention to prevent one of the other serious outcomes listed above (eg, intensive treatment in an emergency room or at home for allergic bronchospasm; blood dyscrasias or convulsions that do not result in hospitalization; or development of drug dependency or drug abuse).

Hospitalization or death due solely to manifestations consistent with typical progression of underlying malignancy will not be considered an SAE.

Criteria for reporting SAEs must be followed for these events. See Section 9.4 for more information on recording and reporting SAEs.

9.3.3. Adverse Events of Special Interest

An AESI (serious or non-serious) is one of scientific and medical concern specific to the sponsor's product or program, for which ongoing monitoring and rapid communication by the investigator to the sponsor can be appropriate. Such an event might warrant further investigation in order to characterize and understand it. Depending on the nature of the event, rapid communication by the trial sponsor to other parties (eg, regulators) might also be warranted (Section 9.4.3).

9.3.4. Infusion Reactions

Infusion reactions are defined as any AE that occurs during the infusion or within 2 hours after the infusion is completed. See Section 7.4.1 for case definition. All infusion reactions must be reported as AEs (defined in Section 9.4.1) and graded using the grading scales as instructed in Section 9.5.1.

9.4. Recording and Reporting Adverse Events

9.4.1. Adverse Events

The investigator (or designee) will seek information on AEs at each patient contact, and record all AEs that occur from the time the informed consent is signed until 105 days (5 half-lives) after the end of study treatment. Prior to initiation of study treatment, only the following categories of AEs should be reported on the AE CRF:

- SAEs
- Non-SAEs associated with a protocol-mandated intervention (eg, AEs related to an invasive procedure such as a biopsy)

Other AEs that occur prior to first treatment should be reported on the medical history CRF.

All AEs after initiation of study treatment and until 105 days (5 half-lives) after the last study treatment, regardless of relationship to study treatment, will be reported on the AE CRF.

Information on follow-up for AEs is provided in Section 9.4.6. Laboratory, vital signs, or ECG abnormalities are to be recorded as AEs as outlined in Section 9.4.5.

9.4.2. Serious Adverse Events

All SAEs, regardless of assessment of causal relationship to study drug, must be reported to the sponsor (or designee) within 24 hours. Refer to the study reference manual for the procedure to be followed.

Information not available at the time of the initial report must be documented in a follow-up report. Substantiating data such as relevant hospital or medical records and diagnostic test reports may also be requested.

In the event the investigator is informed of an SAE that occurs until 105 days (5 half-lives) after the last dose of study treatment, only those SAEs or other AEs of concern deemed by the investigator to be related to study treatment will be reported to the sponsor. The investigator should make every effort to obtain follow-up information on the outcome of a treatment-related SAE until the event is considered chronic and/or stable.

9.4.3. Other Events that Require Accelerated Reporting to Sponsor

The following events also require reporting to the sponsor (or designee) within 24 hours of learning of the event:

Symptomatic Overdose of Study Drug: Accidental or intentional overdose of at least 2 times the intended dose of study drug within the intended therapeutic window, if associated with an AE.

Pregnancy: Although pregnancy is not considered an AE, it is the responsibility of the investigator to report to the sponsor (or designee), within 24 hours of identification, any pregnancy occurring in a female or female partner of a male, during the study or within 105 days (5 half-lives) of the last dose of study drug. Any complication of pregnancy affecting a female study patient or female partner of a male study patient, and/or fetus and/or newborn that meets the SAE criteria must be reported as an SAE. Outcome for all pregnancies should be reported to the sponsor.

Adverse Events of Special Interest: AESIs for this study may include:

- Grade 2 or greater infusion-related reactions
- Grade 2 or greater allergic/hypersensitivity reactions
- Grade 3 or greater irAEs
- An irAE of any grade in a patient previously treated with a PI 3-K inhibitor.

Note: An irAE can occur shortly after the first dose or several months after the last dose of treatment. All AEs of unknown etiology associated with drug exposure should be evaluated to determine possible immune etiology. If an irAE is suspected, efforts should be made to rule out neoplastic, infectious, metabolic, toxin or other etiologic causes prior to labeling an AE as an irAE.

Refer to the study manual for the procedures to be followed.

9.4.4. Reporting Adverse Events Leading to Withdrawal from the Study

All AEs that lead to a patient's withdrawal from the study must be reported to the sponsor's medical monitor within 30 days.

Refer to the study reference manual for the procedures to be followed.

9.4.5. Abnormal Laboratory, Vital Signs, or Electrocardiogram Results

The criteria for determining whether an abnormal objective test finding should be reported as an AE include:

- the test result is associated with accompanying symptoms, and/or
- the test result requires additional diagnostic testing or medical/surgical intervention, and/or
- the test result leads to a change in dosing (outside of protocol-stipulated dose adjustments)
- the test result leads to discontinuation from the study, significant additional concomitant medication, or other therapy

Contact the medical monitor in the event the investigator feels that an abnormal test finding should be reported as an AE, although it does not meet any of the above criteria.

Repeating an abnormal test, in the absence of any of the above conditions, does not constitute an AE. Any abnormal test result that is determined to be an error does not require reporting as an AE.

Evaluation of severity of laboratory abnormalities will be assessed according to the scale outlined in Section 9.5.1.

9.4.6. Follow-up

Information for any non-SAE that starts during the treatment period or within 105 days (5 half-lives) after last treatment will be collected from the time of the event until resolution of the event, or until the patient's last study visit, whichever comes first.

Serious adverse event information will be collected until the event is considered chronic and/or stable.

9.5. Evaluation of Severity and Causality

9.5.1. Evaluation of Severity

The severity of AEs will be graded according to the following scale:

The severity of AEs (including test findings classified as AEs) will be graded using the current version of the NCI-CTCAE grading system. Adverse events not listed in the NCI-CTCAE will be graded according to the following scale:

- 1 (Mild): Mild; asymptomatic or mild symptoms; clinical or diagnostic observations only; intervention not indicated
- 2 (Moderate): Moderate; minimal, local or noninvasive intervention indicated; limiting age-appropriate instrumental Activities of Daily Living (ADL)*
- 3 (Severe): Severe or medically significant but not immediately life-threatening; hospitalization or prolongation of hospitalization indicated; disabling; limiting self-care ADL**
- 4 (Life-threatening): Life-threatening consequences; urgent intervention indicated
- 5 (Death): Death related to AE

* Instrumental ADLs refer to activities such as preparing meals, shopping for groceries or clothes, using the telephone, managing money, etc.

** Self-care ADLs refer to activities such as bathing, dressing and undressing, feeding self, using the toilet, taking medications, and not being bedridden.

If a laboratory value is considered an AE, its severity should be based on the degree of physiological impairment the value indicates.

9.5.2. Evaluation of Causality

Relationship of Adverse Events to Study Drug:

The relationship of AEs to study drug will be assessed by the investigator, and will be a clinical decision based on all available information. The following question will be addressed:

Is there a reasonable possibility that the AE may have been caused by the study drug?

The possible answers are:

Not Related: There is no reasonable possibility that the event may have been caused by the study drug

Related: There is a reasonable possibility that the event may have been caused by the study drug

A list of factors to consider when assessing the relationship of AEs to study drug is provided in [Appendix 8](#).

The investigator should justify the causality assessment of each SAE.

Relationship of Adverse Events to Study Conduct:

The relationship of AEs to study conduct will be assessed by the investigator, and will be a clinical decision based on all available information. The following question will be addressed:

Is there a reasonable possibility that the AE may have been caused by study conduct?

The possible answers are:

Not Related: There is no reasonable possibility that the event may have been caused by study conduct

Related: There is a reasonable possibility that the event may have been caused by study conduct

A list of factors to consider when assessing the relationship of AEs to study conduct is provided in [Appendix 8](#).

The investigator should justify the causality assessment of each SAE.

9.6. Safety Monitoring

The investigator will monitor the safety of study patient at his/her site(s) as per the requirements of this protocol and consistent with current Good Clinical Practice (GCP). Any questions or concerns should be discussed with the sponsor in a timely fashion. The sponsor will monitor the safety data from across all study sites. The medical monitor will have primary responsibility for the emerging safety profile of the compound, but will be supported by other departments (eg, Pharmacovigilance and Risk Management; Biostatistics and Data Management). Safety monitoring will be performed on an ongoing basis (eg, individual review of SAEs) and on a periodic cumulative aggregate basis.

9.7. Investigator Alert Notification

Regeneron (or designee) will inform all investigators participating in this clinical trial, as well as in any other clinical trial using the same investigational drug, of any SAE that meets the relevant requirements for expedited reporting (an AE that is serious, unexpected based on the Investigator's Brochure or this protocol, and has a reasonable suspected causal relationship to the medicinal/study drug).

10. STATISTICAL PLAN

This section provides the basis for the statistical analysis plan (SAP) for the study. The SAP may be revised during the study to accommodate amendments to the clinical study protocol and to make changes to adapt to unexpected issues in study execution and data that may affect the planned analyses. The final SAP will be issued before the database is locked.

In order to describe ORR and DOR, the data cut for primary efficacy analysis will allow responding patients to be followed from onset of response for at least 6 months. Because responses may emerge slowly in BCC patients (Falchook 2016), and the primary endpoint results are not known prior to data cut, the convention in this study will be that all patients will have the opportunity for at least 6 months to develop response. For primary analysis, the last patient in a group will have the opportunity to be followed for approximately 57 weeks, including 27 weeks (cycles 1 to 3) for response, plus an additional 30 weeks (cycles 4 to 6) for DOR. If the last patient(s) has early EOS, the timing of data cut will be determined by the enrollment date of the last enrolled patient who remains on study (first dose + approximately 57 weeks).

An updated analysis of the response duration will be performed after all responding patients have been followed for a minimum of 12 months from onset of response.

An interim analysis of Group 1 patients will be performed at the time of the primary analysis for Group 2. For additional details, please see Section 10.5.

Analysis variables are listed in Section 4.

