5. STUDY DESIGN

5.1. Study Description and Duration

This is a phase 2, non-randomized, 2-group, multi-center study of cemiplimab at a 350 mg dose administered IV Q3W in patients with advanced BCC who experienced progression of disease on HHI therapy, or were intolerant of prior HHI therapy. The study will have 2 groups. Group 1 is for patients with metastatic BCC. Group 2 is for patients with unresectable locally advanced BCC. All patients will undergo screening procedures to determine eligibility within 28 days prior to the initial administration of cemiplimab. There is no randomization or placebo control.

After a screening period of up to 28 days, patients will receive 5 treatment cycles of 9 weeks followed by 4 treatment cycles of 12 weeks for up to 93 weeks of treatment. Each patient will receive a 350 mg dose of cemiplimab IV Q3W. The infusion time for cemiplimab is approximately 30 minutes (\pm 10 minutes). Tumor assessments will be made at the end of each treatment cycle (5 treatment cycles of 9 weeks followed by 4 treatment cycles of 12 weeks). Extensive safety evaluations will occur on day 1 of each cycle, with routine safety evaluations to be conducted at each cemiplimab dosing visit.

A patient will receive treatment until the 93-week treatment period is complete, or until disease progression (PD), unacceptable toxicity, withdrawal of consent, or confirmed CR. Patients with confirmed CR after a minimum of 48 weeks of treatment may elect to discontinue treatment and continue with all relevant study assessments (eg, efficacy assessments). Patients who discontinue study treatment due to PD should return to the clinic 30 days (range: 28 days to 42 days) after the last study treatment to complete the end-of-study (EOS) assessments. After the EOS visit, patients with PD should be followed for survival status until death, loss to follow up, or study termination by the sponsor.

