4.4. Efficacy Variable

4.4.1. Primary Efficacy Variable

The primary objective of the study is to estimate the ORR for mBCC (Group 1) or laBCC (Group 2) according to central review. Objective response rate (ORR) by central review is determined by the proportion of patients with best overall response of CR or PR based on central-reviewed evaluation.

Overall response is determined by RECIST version 1.1 for visceral lesions (Appendix 1 of the protocol), or by modified WHO criteria for skin lesions (Appendix 2 of the protocol), or by the composite response criteria for patients with both visceral and skin lesions (Appendix 2 of the protocol) at each time point at which a response assessment occurs.

Best overall response (BOR) is determined once all the overall response data for the patient are known. The best overall response is the best response recorded during the study:

- Best overall response of CR or PR must be confirmed by consecutive evaluations of overall response of CR or PR at time points at least 4 weeks apart.
- Best overall response of SD must have met the response SD criteria at least once ≥ 39 days (6 weeks – 3 days) after start of study treatment. Best overall response of (early) PD does not require confirmation using the RECIST or the composite response criteria.
- The best overall response for patients who do not have any post-baseline tumor assessment will be not evaluable (NE). Patients with best overall response of NE will be considered as not reaching an objective response of CR or PR.

- Patients with inoperable BCC at baseline who are rendered operable with clear margins will be deemed to have experienced PR.

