5.8.2. Analysis of Secondary Efficacy Variables

ORR derived from the overall response that is based on investigator review will be analyzed similarly as primary efficacy variable.

DOR: The distribution of DOR will be estimated using the Kaplan-Meier method. The median DOR along with its 95% CI will be presented by group and Kaplan-Meier estimates with 2-sided 95% CIs at specific time points (for example, 6, 12, 18 and 24 months) will be summarized. The Kaplan-Meier curves will be displayed by group. DOR will also be summarized descriptively by range. Number and percentage of patients with DOR at specific time periods of interest (e.g., $>=3$ months, $>=6$ months, $>=12$ months, $>=18$ months, etc.) will be summarized by group.

PFS: The distribution of PFS will be estimated using the Kaplan-Meier method. The median PFS along with its 95% CI will be presented by group and Kaplan-Meier estimates with 2-sided 95% CIs at specific time points (for example, 6, 12, 18 and 24 months) will be summarized. The Kaplan-Meier curves will be displayed by group.

OS: The distribution of OS will be estimated using the Kaplan-Meier method. The median OS along with its 95% CI will be presented by group and Kaplan-Meier estimates with 2-sided 95% CIs at specific time points (for example, 6, 12, 18 and 24 months) will be summarized. The Kaplan-Meier curves will be displayed by group. A variant of OS defined by censoring patients at the start date of subsequent therapy will be summarized and displayed by Kaplan-Meier approach as a sensitivity analysis.

TTR will be summarized descriptively by group and at specific time periods of interest (e.g., <2 months, 2 to 4- months, 4 to 6- months, $>=6$ months).

CR rate, DCR and dDCR will be summarized by group and the corresponding 2-sided 95% exact binomial confidence intervals will be derived using the Clopper-Pearson method.

The duration of response and the best percentage change from baseline in target lesions will be presented by swimmer plot and waterfall plot respectively.

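### The 57-week data cut secures 6 months of response follow-up only for responses that start by week 27, and the raw DOR percentages need a stated denominator and time origin

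*Protocol*

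**What the plan says.** Protocol section 10 states that "the data cut for primary efficacy analysis will allow responding patients to be followed from onset of response for at least 6 months"; SAP section 5 repeats this. Both then give the rule that sets the cut, under which "the last patient in a group will have the opportunity to be followed for approximately 57 weeks". They divide that period between the two purposes, "including 27 weeks (cycles 1 to 3) for response, plus an additional 30 weeks (cycles 4 to 6) for DOR". The protocol gives a reason for the response window: "Because responses may emerge slowly in BCC patients". SAP section 8 applies the same 57-week rule to the Group 1 interim analysis.

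Tumor assessments fall at the end of each cycle, with "5 treatment cycles of 9 weeks followed by 4 treatment cycles of 12 weeks" (Protocol 5.1). Responses are not limited to the first 27 weeks. SAP 4.4.1 says "The best overall response is the best response recorded during the study", and a CR or PR "must be confirmed by consecutive evaluations of overall response of CR or PR at time points at least 4 weeks apart".

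SAP 4.4.2 defines DOR from first documentation of response, only for patients whose best overall response is CR or PR. Ongoing responders are censored at their last evaluable assessment. The same section ends with one formula for all its time-to-event variables, which counts days from first study treatment.

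SAP 5.8.2 plans Kaplan-Meier estimates of DOR, including values at 6, 12, 18 and 24 months, and also: "Number and percentage of patients with DOR at specific time periods of interest", with at least 3, 6, 12 and 18 months as examples. It gives neither a denominator nor a rule for censored responders. Both documents plan a DOR update once every responder has 12 months from onset.

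**The concern.** The follow-up sentence carries no condition, but the rule beneath it meets the sentence only for early onsets. The plan itself expects slow responses, and two scheduled assessments (weeks 36 and 45) lie between the end of the response window and the cut. A response first seen at either one enters the ORR and the DOR set, with less than 6 months behind it in late-enrolled patients.

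The raw percentages raise a second, separate issue. If every responder is in the denominator, a patient still responding but followed briefly is treated like one whose response has ended. The figure then mixes follow-up time with durability.

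The SAP calls the trial pivotal (2.1) and records that post-treatment follow-up was lengthened after regulatory feedback, to capture DOR more stringently (1.2.5). A minimum follow-up statement and durability percentages are therefore likely to be reported and read at face value.

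**Working it through.** **The plan's own figure.** Cycles 1 to 3 are 3 × 9 = 27 weeks. Cycles 4 to 6 are 9 + 9 + 12 = 30 weeks. The total is 57 weeks, as stated. With a month of 30.44 days, 6 months is 6 × 30.44 / 7 = 26.1 weeks, so 30 weeks (6.9 months) is enough for a week-27 onset.

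**Follow-up at the cut, last-enrolled patient.** Scheduled assessments fall at weeks 9, 18, 27, 36, 45, 57, 69, 81 and 93. Follow-up = 57 − onset week; months = weeks × 7 / 30.44.

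| Onset week | Weeks to cut | Months |
|---|---|---|
| 9 | 48 | 11.0 |
| 18 | 39 | 9.0 |
| 27 | 30 | 6.9 |
| 36 | 21 | 4.8 |
| 45 | 12 | 2.8 |

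By calendar, the latest onset with 6 months is 57 − 26.1 = week 30.9; among scheduled assessments that means week 27. A week-27 onset also has little slack: if the week-57 assessment falls after the cut, censoring is at week 45, giving 18 weeks (4.1 months).

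**Which patients are affected.** By calendar time, a week-36 onset falls short in patients first dosed within 36 + 26.1 − 57 = 5.1 weeks of the last patient, and a week-45 onset within 45 + 26.1 − 57 = 14.1 weeks. DOR is censored at an assessment, though, so 6 months must be visible at one. For a week-36 onset the first such assessment is week 69 (69 − 57 = 12 weeks); for a week-45 onset it is week 81 (24 weeks).

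**The 12- and 18-month thresholds.** Twelve months is 52.2 weeks. Even a week-9 onset in the last-enrolled patient has only 48 weeks. With a week-9 onset, 12 months first shows at week 69 and 18 months at week 93. The limit at these thresholds comes from the cut itself, whatever the onset time.

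**Size of the effect on the raw percentages.** The documents give no accrual pattern, onset distribution or expected DOR, so these were assumed and the range is shown. Each scenario simulated 400,000 responders on the protocol schedule:

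- uniform accrual over 12, 18 or 24 months;
- exponential DOR beyond the 4-week confirmation, median 9.5 months (the historical hedgehog-inhibitor figure for locally advanced disease in Protocol 1.1) or 24 months;
- onset at weeks 9/18/27/36/45/57 in shares 50/25/15/5/3/2% (early) or 30/22/18/13/10/7% (slow).

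The denominator is all responders and DOR runs from onset.

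| Threshold | Raw share too low by | Smallest gap (raw vs complete follow-up) | Largest gap | Kaplan-Meier error |
|---|---|---|---|---|
| 6 months | 1 to 11 points | 0.77 vs 0.79 | 0.80 vs 0.90 | within 0.1 point |
| 12 months | 9 to 37 points | 0.39 vs 0.48 | 0.38 vs 0.75 | within 2.1 points |
| 18 months | 13 to 55 points | 0.18 vs 0.32 | 0.08 vs 0.63 | within 4 points |

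Responders with under 6 months of follow-up at the cut make up 2 to 4% (early onset) or 6 to 12% (slow onset).

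**Time origin.** If the SAP 4.4.2 formula is applied to DOR as written, counting from first treatment, the raw shares become too high at 6 months (0.96 to 0.99 against 0.77 to 0.91) and at 12 months (0.68 to 0.89 against 0.48 to 0.75). At 18 months the direction varies by scenario (for example 0.35 against 0.32, but 0.40 against 0.63).

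**Primary test.** The ORR rule does not use DOR. The thresholds of 14/50 and 24/80 give power 0.852 and 0.855, matching the stated 85%.

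**The case against.** The strongest reply is that the paragraph already shows its own limit. The split into 27 and 30 weeks follows the general sentence closely, and a careful reader can see that the DOR window is built for onset by week 27. Kaplan-Meier is the planned DOR method and deals with the censoring; the raw counts are an added descriptive line. The 12-month update is anchored to actual onset, so late responders are covered then. No hypothesis test rests on DOR.

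Most of this stands and limits the point. Three gaps remain: the general sentence is unqualified while later responses count; the raw percentages have no stated denominator; and the update comes after the primary analysis, largely settling the 6- and 12-month shares but not the 18-month one.

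The reply also rules out some stronger readings that a reader might infer:

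- *That the cut fails responders in general.* It does not: onset by week 27 gets at least 30 weeks.
- *That a first response at week 57 shows zero follow-up.* In the last-enrolled patient it cannot be confirmed by the cut, so that patient is not in the DOR set and is not part of the shortfall.
- *That the durability percentages are understated outright.* The SAP fixes neither the denominator nor, consistently, the time origin, so the direction is conditional.
- *That a week-9 responder's 11.0 months breaks a promise.* The plan never promises 12 months at the primary cut.

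**Conclusion.** The point holds in a limited form. The 6-month statement is true for onset by week 27 and not guaranteed after that: in the last-enrolled patient a week-36 or week-45 onset has 4.8 or 2.8 months. This part rests only on the documents' schedule and definitions.

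The raw DOR percentages would be too low at the primary cut if all responders are counted and DOR runs from onset. The effect is small at 6 months and larger at 12 and 18 months, where it reflects censoring at the cut rather than mainly late onset. Its size depends on assumed accrual, onset and DOR. The documents do not support reading this as a flaw in the DOR analysis as a whole, or in the primary result: Kaplan-Meier and the later update are already planned, and ORR and its test are unaffected. It should be corrected because the remedy is cheap and these figures are likely to be reported.

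**What to change.** 1. In Protocol section 10 and SAP section 5, state that the 6-month minimum applies to responders with onset by week 27. Make the same change in SAP section 8 for the Group 1 interim analysis.
2. In SAP 5.8.2, give the raw number and percentage at each DOR threshold only among responders whose potential follow-up (onset to data cut) reaches that threshold, and show the denominator. Alternatively, drop the raw shares and rely on the Kaplan-Meier values already planned at 6, 12, 18 and 24 months.
3. In SAP 4.4.2, exempt DOR from the formula that counts from first treatment and give it a formula that counts from onset, in line with its own definition.

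The cost is SAP and protocol wording, and smaller denominators for any raw percentages kept. No extra visits, data or patients are needed.
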